10.6.2 Number of Days in the Hospital

The date of each hospital admission and discharge will be collected for each subject. The number of days when subjects are still alive and out of hospital during the first 30 Days of the study will be summarized by treatment group. We will explore nonparametric comparisons of days in hospital after randomization between arms.

10.6.3 Number of Days in the ICU and Days on Mechanical Ventilation

The analysis will be the same as the number of days in the hospital

10.8 PK Analysis

Descriptive statistics will include mean, standard deviation, minimum, median, and maximum for PK parameters and concentrations.

The relationship between exposure and response will be assessed based on the PK data and efficacy/safety data collected in this study. The methods will include a population PK modeling approach using the sparse data collected. The details of population PK modeling and full results of the exposure response analyses will be reported in a separate document, and the summary of key findings will be included in the clinical study report.

11 ADMINISTRATIVE CONSIDERATIONS

11.1 Monitoring of the Study

The site monitor, as a representative of CalciMedica, will closely follow the conduct of the study. The site monitor will collaborate with the study site to maintain necessary communication with the PI and his/her study staff through telephone, email, etc.. The site monitor will maintain current knowledge of each site's study activity by observing the conduct of the study at the site, reviewing study records and source documentation (remote monitoring), performing study drug accountability, reviewing the site files (i.e. regulatory documentation, training records, etc.) and discussing the conduct of the study with the PI and his/her study staff.

11.2 Inspection of Records

The PI, his/her study staff and the study site will provide access to all study records to assist study-related monitoring and audits, Institutional Review Board/Ethics Committee/Research Ethics Board reviews, and regulatory inspections. In the event of an audit, the PI agrees to allow CalciMedica or its representatives and relevant regulatory authorities access to all study records.

If any regulatory agency schedules an audit, the PI should promptly notify CalciMedica or its representatives and promptly forward to CalciMedica copies of any audit reports he/she receives.

11.3 Study Record Retention

The PI or his/her study staff must retain essential documents for at least 2 years after the last approval of a marketing application in an ICH region. They should retain these documents longer if required because of regulatory requirements or because of an agreement with CalciMedica.

11.4 Study Conduct: Good Clinical Practice and Declaration of Helsinki

CalciMedica will design the clinical study, shall implement it, and report it in accordance with the ICH Harmonized Guideline for Good Clinical Practice, with applicable local regulations (e.g., European Directive 2001/83/EC and US Code of Federal Regulations Title 21), and with the ethical principles laid down in the Declaration of Helsinki.

The PI agrees to conduct the study in accordance with the ICH Guideline for Good Clinical Practice, with applicable local regulations (e.g., European Directive 2001/83/EC and US Code of Federal Regulations Title 21) and with the principles of the Declaration of Helsinki. The PI must conduct all aspects of this study in accordance with all national, state and local laws or regulations.

11.5 Responsibilities of the Investigator and the IRB/EC

A properly constituted IRB/EC must review and approve the protocol and the proposed informed consent form before the start of the study at the site. The PI or his/her study staff must provide

CalciMedica or its designee a signed and dated statement that the IRB/EC has approved the protocol and the informed consent form before consenting patients for the study. Prior to starting the study, the PI will sign a protocol signature page confirming that he/she will conduct the study in accordance with this protocol and he/she will give CalciMedica or its designee and regulatory authorities access to all relevant data and records.

The IRB/EC chairperson or designee must sign all IRB/EC approvals and must identify the IRB/EC by name and address, the clinical protocol, and the date of approval.

The PI is responsible for obtaining reviews of the clinical research at intervals specified by the IRB/EC. The specified intervals should not exceed 1 year. The PI must supply CalciMedica or its designee written documentation of the reviews of the clinical research.

11.6 Confidentiality

All laboratory specimens, evaluation forms, reports, and other records will be identified in a manner designed to maintain patient confidentiality. All records will be kept in a secure storage area with limited access. Clinical information will not be released without the written permission of the patient (or the patient's legal representative) except as necessary for monitoring and auditing by CalciMedica or its designee, inspections by relevant regulatory authorities, or reviews by the IRB/EC.

The PI, all study staff and all co-workers involved in the study may not disclose or use for any purpose other than the conduct of the study any data, record or other unpublished confidential information disclosed to them for the purpose of the study. They must obtain prior written agreements from CalciMedica or its designee for the disclosure of any said confidential information to other parties.

11.7 Modification of the Protocol

Any changes that arise after the approval of the protocol must be documented as protocol amendments. Amendments (substantial/non-substantial) require regulatory approval and IRB/EC approval or notification. Only after approval by CalciMedica, the PI, the IRB/EC, and if applicable the regulatory authorities, will the protocol amendments become effective. In cases when the protocol is amended to enhance patient safety, the amendment may be implemented but must be immediately submitted to the IRB/EC and regulatory authorities.

The revision number and date of the amendment will be recorded on the title page of the protocol.

The PI is responsible for informing the IRB/EC of all problems involving risks to patients. In case of urgent safety measures, CalciMedica or its designee will immediately notify the PIs and relevant regulatory authorities.

11.8 Informed Consent

Because the study will be conducted under a United States Investigational New Drug Application, informed consent that is in compliance with Title 21 of the United States Code of Federal Regulations (CFR) Part 50 will be obtained from each patient or LAR before the patient enters the study or before any unusual or non-routine procedure is performed. For sites outside the United States, the signed informed consent form will be obtained in compliance with local regulations, ICH E6 (R2) and the principles of the Declaration of Helsinki.

CalciMedica or its designee may provide to the PI or his/her study staff an informed consent form template. The informed consent form must be reviewed by CalciMedica or its designee before the PI or his/her study staff submits it to the IRB/EC. After CalciMedica or its designee review the informed consent form, the PI or his/her study staff will submit it to the IRB/EC for review and approval. If the informed consent form is revised during the course of the study, CalciMedica or its designee must agree with revisions before the PI or his/her study staff submits it to the IRB/EC. The study staff must provide CalciMedica or its designee a copy of the revised informed consent form after IRB/EC approves it. All patients or LARs affected by the revision must sign the revised informed consent form after the IRB/EC approves it.

Before enrolling in the study, each prospective patient or LAR will receive a full explanation of the study and review the approved informed consent form. Once the PI or designee is assured that the patient or LAR understands the implications of participating in the study, he/she will ask the patient or LAR to give consent for the patient to participate in the study by signing the informed consent form.

A patient may participate in the study only after providing consent using an IRB/EC approved informed consent form. A LAR of the patient may provide informed consent on behalf of the patient under conditions authorized by local laws and regulations. The patient or LAR must provide informed consent before the patient undergoes any study-specific procedures described in the protocol. The PI or designee will provide a copy of the informed consent form to the patient and/or LAR. The process of obtaining informed consent must also be documented in the patient source documents.

11.9 Protocol Violations and Deviations

The PI or designee must document any protocol deviation or violation. Reporting of protocol deviations and violations to the appropriate IRB/EC is the responsibility of the PI and must follow the applicable IRB/EC guidelines.

Major protocol deviations are a subset of protocol deviations that might significantly affect the completeness, accuracy, and/or reliability of the study data or that might significantly affect a patient's rights, safety, or well-being.

If there is an immediate hazard to the patient, the PI may deviate from the protocol without prior approval from CalciMedica or its designee and the IRB/EC but must notify CalciMedica or its designee and IRB/EC of the deviation as soon as he/she is able to do so.

11.10 Financial Disclosure

PIs and sub-investigators are required to document financial disclosure information prior to conducting any study procedures. In addition, the PIs and sub-investigators must provide CalciMedica or its designee with updated information if any relevant changes occur during the course of the study and for one year following the completion of the study.

Any PIs, sub-Investigators or study staff with a vested financial interest in the success of the study may not participate in the study.

11.11 Sponsor Obligations

CalciMedica or designee is not financially responsible for further testing/treatment of any medical condition that may be detected during Screening. In addition, CalciMedica is not financially responsible for the treatment of the patient's underlying disease.

11.12 Investigator Documentation

The PI will be asked to comply with ICH E6 (R2) 8.2 and title 21 CFR by providing to CalciMedica or designee the following documents:

- The IRB/EC approval of the protocol
- The IRB/EC approved informed consent form
- Any written information regarding the study that will be provided to the patient or LAR
- A Form FDA 1572, fully executed, and all updates on new fully executed Form FDA 1572 (Unless granted an exemption by the FDA and in compliance with local regulations)
- Curricula Vitae for the PI and each sub-Investigator listed on Form FDA 1572. Evidence of licensure must be noted on the Curricula Vitae or a copy of the license must be provided. The Curricula Vitae must have been updated by the PI and sub-Investigators within 3 years before study start-up to indicate that the documents are accurate and current
- Completed financial disclosure forms to allow CalciMedica or designee to submit complete and accurate certification or disclosure statements required under US Title 21 CFR 54. In addition, the PI and sub-Investigators must provide to CalciMedica or designee a commitment to update this information promptly if any relevant changes occur during the course of the study and for 1 year following completion of the study
- Laboratory certifications and normal ranges for any laboratories used by the site for the conduct of the study

11.13 Clinical Study Insurance

CalciMedica has subscribed to an insurance policy, covering in its terms and provisions its legal liability for injuries caused to participating persons and arising out of this research that is

performed strictly in accordance with the scientific protocol as well as with applicable law and professional standards.

11.14 Use of Information

All information supplied by CalciMedica to the PI and his/her study staff is privileged and confidential. The PI and his/her study staff agree to use this information to accomplish the study and not to use it for other purposes without consent from CalciMedica. Furthermore, the PI and his/her study staff are obligated to provide CalciMedica with complete data obtained during the study. The information obtained from the clinical study will be used towards the development of Auxora, and may be disclosed to regulatory authorities, other Investigators, corporate partners or consultants as required.

11.15 Publications

CalciMedica Inc. reserves the right to review all planned communications and manuscripts based on the results of this study. This reservation of the right is not intended to restrict or hinder publication or any other dissemination of study results, but rather to allow CalciMedica to confirm the accuracy of the data, to protect proprietary information, and to provide comments based on information that may not yet be available to the study investigators. CalciMedica Inc. supports communication and publication of study results whatever the findings of the study. CalciMedica Inc. also encourages disclosure of any conflict of interest from all authors or investigators when manuscripts are submitted for publication.

11.16 Independent Data Monitoring Committee

An IDMC will be convened and will monitor safety for this study on an ongoing basis. An IDMC charter will govern the IDMC and will describe the scope of responsibilities of the IDMC. If the IDMC recommends alteration of the dosing regimen because of safety issues, the FDA and other regulatory agencies will be notified as appropriate. The IDMC responsibilities include protecting the safety of the study patients and making recommendations to CalciMedica concerning the conduct of the study.

Appendix 1. Imputed $\text{PaO}_2/\text{FiO}_2$ Ratio

FiO_2	SpO_2																		
	0.7	0.75	0.8	0.81	0.82	0.83	0.84	0.85	0.86	0.87	0.88	0.89	0.9	0.91	0.92	0.93	0.94	0.95	0.96
0.21	174	191	211	216	221	226	232	238	245	252	260	269	279	291	304	319	337	360	390
0.24	153	167	185	189	193	198	203	208	214	221	228	236	244	254	266	279	295	315	341
0.27	136	148	164	168	172	176	180	185	190	196	202	209	217	226	236	248	262	280	303
0.28	132	143	157	161	164	168	175	179	182	189	196	204	211	218	229	239	254	271	293
0.3	122	133	148	151	155	158	162	167	171	177	182	189	196	203	213	223	236	252	273
0.32	116	125	138	141	144	147	153	156	159	166	172	178	184	191	200	209	222	238	256
0.35	105	114	127	129	132	136	139	143	147	151	156	162	168	174	182	191	202	216	234
0.36	103	111	122	125	128	131	136	139	142	147	153	158	164	169	178	186	197	211	228
0.4	92	100	111	113	116	119	122	125	129	132	137	141	147	153	159	168	177	189	205
0.44	84	91	100	102	105	107	111	114	116	120	125	130	134	139	145	152	161	173	186
0.45	81	89	98	101	103	106	108	111	114	118	121	126	130	136	142	149	157	168	182
0.5	73	80	89	91	93	95	97	100	103	106	109	113	117	122	128	134	142	151	164
0.55	67	73	81	82	84	86	89	91	94	96	99	103	107	111	116	122	129	138	149
0.6	61	67	74	76	77	79	81	83	86	88	91	94	98	102	106	112	118	126	136
0.65	56	62	68	70	71	73	75	77	79	81	84	87	90	94	98	103	109	116	126
0.7	52	57	63	65	66	68	70	71	73	76	78	81	84	87	91	96	101	108	117
0.75	49	53	59	60	62	63	65	67	69	71	73	75	78	81	85	89	94	101	109
0.8	46	50	55	57	58	59	61	63	64	66	68	71	73	76	80	84	89	95	102
0.85	43	47	52	53	55	56	57	59	61	62	64	67	69	72	75	79	83	89	96
0.9	41	44	49	50	52	53	54	56	57	59	61	63	65	68	71	74	79	84	91
0.95	39	42	47	48	49	50	51	53	54	56	58	60	62	64	67	71	75	80	86
1	37	40	44	45	46	47	49	50	51	53	55	57	59	61	64	67	71	76	82

Adapted from [Fowler et al., 2019](#)

Appendix 2. Schedule of Events

	Screen	If Eligible, Baseline Assessment	R	0 hour	24 (±2) hours	48 (±2) hours	72 (±2) hours	96 (±2) hours	120 (±2) hours	144 (±2) hours	168 hours -Discharge ^e	Day 30 ^f	Day 60 ^f
Informed Consent	X												
Weight and Height	X												
Vital Signs ^a	X				X	X	X	X	X	X			
P/F ratio	X				X	X	X	X	X	X			
QTcF	X				X	X	X	X	X	X			
SARS-CoV-2 testing	X												
Serum Pregnancy Test in WOCBP	X												
Daily Laboratory Monitoring		X			X	X	X	X	X	X			
Nasopharyngeal PCR ^h		X					X ^{Cohort 1,3}	X ^{Cohort 2,3}					
BAL ^g		X					X ^{Cohort 1,3}	X ^{Cohort 2,3}					
Blood for biomarkers		X					X ^{Cohort 1,3}	X ^{Cohort 2,3}					
PK Analysis				X ^b	X ^c	X ^c	X ^c	X ^d		X			
AE/SAE/Mortality Assessment					X	X	X	X	X	X	X	X	X
Concomitant Medications				X	X	X	X	X	X	X			
Randomize patient			X										
Study Drug Administration				X ^{Cohorts 1,2,3}	X ^{Cohorts 1,2}	X ^{Cohorts 1,2}	X ^{Cohort 2}						
Study Drug Continuous Infusion ⁱ				X ^{Cohort 3}	X ^{Cohort 3}	X ^{Cohort 3}	X ^{Cohort 3}						

Hospitalized patients will complete all assessments. All patients will complete the Day 30 and Day 60 assessment.

- a. Vital Signs will include temperature, heart rate, respiratory rate, systolic blood pressure, and diastolic blood pressure.
- b. Draw blood sample for PK after finishing the infusion of Auxora (+30 minutes).
- c. For Cohorts 1 and 2 draw blood sample for PK prior to the infusion of Auxora (-2 hours). For Cohort 3, draw PK every 24 hours from SFISD up to hour 72
- d. Draw PK at the end of the continuous infusion (+30 minutes)
- e. In patients who remain hospitalized, AE/SAE/Mortality assessments will be made every 48 hours starting at 168 hours and until Discharge or Day 30, whichever comes first. If patients have been discharged, no follow up during this period is needed; ongoing SAEs should be followed reviewed at Day 30 and Day 60.
- f. Day 30 will be a phone call assessment for patients discharged prior to Day 25. Patients discharged at Days 25,26,27,28,29 will perform the Day 30 assessment before leaving the hospital. Day 60 will be a phone call assessment for patients discharged prior to Day 55 and an inpatient assessment for patients hospitalized between Days 55 and 60.
- g. BAL fluid will be used for flow cytometry, single cell RNA sequencing, and chemokine/biomarker panel. On the post infusion BAL fluid, CM4620 levels will be determined.
- h. Nasopharyngeal swabs will be performed weekly until SARS-CoV-2 RNA is no longer detected
- i. Continuous infusion starts at the end of the first infusion and continues for 96 hours. Infusion ends 100 hours after SFISD

**Clinical Trial Number: NCT04661540**

# **A Single-Blind Dose-Ranging Pharmacodynamic Study of Auxora for the Treatment of Patients with Critical COVID 19 Pneumonia**

**CM4620-205**

## **STATISTICAL DESIGN AND POWER**

### **INTRODUCTION**

This document outlines the proposed analyses for the Auxora trial. This phase II, single center, single-blind, randomized controlled trial is designed to assess the pharmacodynamic response of bronchoalveolar lavage (BAL) T cell/monocyte subsets and chemokine release to various doses of Auxora in patients with critical COVID-19 pneumonia. The purpose of this document is to provide detail regarding the statistical analysis plan (SAP) for this study. Northwestern University Data Analysis and Coordinating Center (NUDACC) will spearhead overall SAP development and maintain all versions. NUDACC will also implement these analyses as specified, and will ensure appropriate inference and interpretation in dissemination materials.

### **STUDY OBJECTIVES**

#### Primary

- To assess the pharmacodynamic response of bronchoalveolar lavage (BAL) T cell/monocyte subsets and chemokine release to various doses of Auxora in patients with critical COVID-19 pneumonia

#### Secondary

- To assess the safety and tolerability of Auxora in patients with critical COVID-19 pneumonia
- To assess the serum and BAL pharmacokinetic profile of various doses of Auxora in patients with critical Covid-19 pneumonia

### **STUDY METHODS**

#### Trial Design

This will be a single center, prospective randomized trial of patients  $\geq$  18 years of age critical SARS-CoV-2 infection. The patient will not know if they are receiving Auxora or Placebo. The first 4 patients will be enrolled in Cohort 1 and randomized 3:1 to Auxora or Placebo. If dose escalation occurs, the next 8 patients will be enrolled in Cohort 2 and randomized 3:1 to Auxora or Placebo. If dose escalation continues, the next 8 patients will be enrolled in Cohort 3 and randomized 3:1 to Auxora or Placebo. The decision to escalate dosing will be made by CalciMedica in consultation with the PI after the review of safety events in Cohorts 1 and 2.

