[figure not shown]
CM4620-205 Protocol

A Single-Blind Dose-Ranging Pharmacodynamic Study of Auxora for the Treatment of Patients with Critical COVID-19 Pneumonia

Version: 3.1

Issue Date: November 18, 2021

Clinical Trial Number: NCT04661540

CalciMedica

CM4620-205

A Single-Blind Dose-Ranging Pharmacodynamic Study of Auxora for the Treatment of Patients with Critical COVID-19 Pneumonia

Sponsor: CalciMedica, Inc.
[name]
[name]

Sponsor Medical Contact: [name]
[contact] – Mobile
[contact] – Email

FOR QUALIFIED INVESTIGATORS AND THEIR IRB/EC ONLY

Version: 3.1

Issue Date: November 18, 2021

Confidentiality Statement

The information contained in this document is confidential and proprietary property of CalciMedica, Inc. Any distribution, copying, or disclosure is strictly prohibited unless federal regulations or state law requires such disclosure. Prior written authorization of CalciMedica, Inc. is required for any disclosure or use of the information contained herein. Persons to whom the information is disclosed must know that it is confidential and that it may not be further disclosed by them.

SPONSOR APPROVAL AND SIGNATURE PAGE

[name] MD
Chief Medical Officer

01-December-2021

Date

[name] Ph.D.
Chief Scientific Officer

01-December-2021

Date

SYNOPSIS

Protocol Number:	CM4620-205														
Protocol Title for Part 2:	A Single-Blind Dose-Ranging Pharmacodynamic Study of Auxora for the Treatment of Patients with Critical COVID-19 Pneumonia														
Sponsor:	CalciMedica, Inc. [name] [name] USA														
Study Phase:	2														
Number of Patients and Sites:	Up to 32 patients with confirmed COVID-19 pneumonia on invasive mechanical ventilation randomized at up to two sites.														

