	
• Third degree or high grade AV block; or• Polymorphic Ventricular Tachycardia; 
If one of the listed safety events occurs in a patient who is receiving Auxora in Cohort 1 but the event is not thought to be dose limiting, 4 additional patients will be enrolled in Cohort 1 and randomized 3:1 to Auxora versus Placebo for a total of 8 patients enrolled in the cohort, 6 randomized to Auxora and 2 to Placebo. The PI and CalciMedica will consult after all 8 patients are enrolled to determine if dose escalation to Cohort 2 will occur. If one of the listed safety events occurs in a patient who is receiving Auxora in Cohort 1 and the event is dose limiting, further dosing will not occur using the planned dose regimens but may occur using a regimen that provides lower total exposure of drug.
 
If one of the listed safety events occurs in a patient who is receiving Auxora in Cohort 2 but the event is not thought to be dose limiting, 4 additional patients will be enrolled in Cohort 2 and randomized 3:1 to Auxora versus Placebo for a total of 8 patients enrolled in the cohort, 6 randomized to Auxora and 2 to Placebo. The PI and CalciMedica will consult after all 8 patients are enrolled to determine if dose escalation to Cohort 3 will occur. If one of the listed safety events occurs in a patient who is receiving Auxora in Cohort 2 and the event is dose limiting, further dosing will not occur in either Cohorts 2 or 3. 4 additional patients may be enrolled in Cohort 1 and randomized 3:1 to Auxora versus Placebo. The 4 additional patients in Cohort 1 will receive a dose regimen of an initial infusion followed by continuous infusion for 48 hours.
 
If one of the listed safety events occurs in a patient who is receiving Auxora in Cohort 3 but the event is not felt to be dose limiting, 4 additional patients will be enrolled in Cohort 3 and randomized 3:1 to Auxora versus Placebo for a total of 12 patients enrolled in the cohort, 9 randomized to Auxora and 3 to Placebo. If one of the listed safety events occurs in a patient who is receiving Auxora in Cohort 3 and the event is dose limiting, further dosing will not occur in Cohort 3. 4 additional patients may be enrolled in Cohort 2 and randomized 3:1 to Auxora versus Placebo. The 4 additional patients in Cohort 2 will receive a dose regimen of an initial infusion followed by continuous infusion for 72 hours.
 
A study physician or appropriately trained delegate will perform assessments at Screening, immediately prior to the SFISD, and then every 24 hours (± 1 hours) until 240 hours after the SFISD. After 240 hours from the SFISD, the patient will be assessed q48 hours until Day 30 after the SFISD, or until discharge if earlier. Patients who are discharged before Day 25 after the SFISD will be followed-up at Day 30 (± 5 days). Patients will be followed up at Day 60 (± 5 days). for a safety and mortality assessment.

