3 INVESTIGATIONAL PLAN

3.1 Study Design

This will be a single-blind study where the patient will not know if they are receiving Auxora or Placebo. The first 4 patients will be enrolled in Cohort 1 and randomized 3:1 to Auxora or Placebo. If dose escalation occurs, the next 4 patients will be enrolled in Cohort 2 and randomized 3:1 to Auxora or Placebo. If dose escalation continues, the next 8 patients will be enrolled in Cohort 3 and randomized 3:1 to Auxora or Placebo. The decision to escalate dosing will be made by CalciMedica in consultation with the PI after the review of safety events in Cohorts 1 and 2.

Consultation between the PI and CalciMedica will occur if any patient receiving Auxora in Cohorts 1, 2 or 3 experiences one of the cardiac conduction events listed below during the 144 hours after the Start of the First Infusion of Study Drug (SFISD):

- QTcF interval of \geq 500 msec; or
- QTcF prolongation of \geq 60 msec as compared to baseline; or
- Mobitz Type II second degree atrioventricular (AV) block; or
- Third degree or high grade AV block; or
- Polymorphic Ventricular Tachycardia;

If one of the listed safety events occurs in a patient who is receiving Auxora in Cohort 1 but the event is not thought to be dose limiting, 4 additional patients will be enrolled in Cohort 1 and randomized 3:1 to Auxora versus Placebo for a total of 8 patients enrolled in the cohort, 6 randomized to Auxora and 2 to Placebo. The PI and CalciMedica will consult after all 8 patients are enrolled to determine if dose escalation to Cohort 2 will occur. If one of the listed safety events occurs in a patient who is receiving Auxora in Cohort 1 and the event is dose limiting, further dosing will not occur using the planned dose regimens but may occur using a regimen that provides lower total exposure of drug.

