If one of the listed safety events occurs in a patient who is receiving Auxora in Cohort 2 but the event is not thought to be dose limiting, 4 additional patients will be enrolled in Cohort 2 and randomized 3:1 to Auxora versus Placebo. The PI and CalciMedica will consult after all patients are enrolled to determine if dose escalation to Cohort 3 will occur. If one of the listed safety events occurs in a patient who is receiving Auxora in Cohort 2 and the event is dose limiting, further dosing will not occur in either Cohorts 2 or 3. 4 additional patients may be enrolled in Cohort 1 and randomized 3:1 to Auxora versus Placebo. The 4 additional patients in Cohort 1 will receive a dose regimen of an initial infusion followed by continuous infusion for 48 hours.

If one of the listed safety events occurs in a patient who is receiving Auxora in Cohort 3 but the event is not felt to be dose limiting, 4 additional patients will be enrolled in Cohort 3 and randomized 3:1 to Auxora versus Placebo for a total of 12 patients enrolled in the cohort, 9 randomized to Auxora and 3 to Placebo. If one of the listed safety events occurs in a patient

who is receiving Auxora in Cohort 3 and the event is dose limiting, further dosing will not occur in Cohort 3. 4 additional patients may be enrolled in Cohort 2 and randomized 3:1 to Auxora versus Placebo. The 4 additional patients in Cohort 2 will receive a dose regimen of an initial infusion followed by continuous infusion for 72 hours.

A study physician or appropriately trained delegate will perform assessments at Screening, immediately prior to the SFISD, and then every 24 hours (± 1 hours) until 240 hours after the SFISD. After 240 hours from the SFISD, the patient will be assessed q48 hours until Day 30 after the SFISD, or until discharge if earlier. Patients who are discharged before Day 25 after the SFISD will be followed-up at Day 30 (± 5 days). Patients will be followed up at Day 60 (± 5 days) for a safety and mortality assessment. This assessment will be conducted by phone for patients discharged prior to Day 55. The Day 60 assessment will be completed as a final inpatient safety assessment for patients who remain hospitalized or are discharged from the hospital on Days 55-59.

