#### Interim Analysis and Stopping Guidelines

As this is a dose-escalation study, Consultation between the PI and CalciMedica will occur if any patient receiving Auxora in Cohorts 1, 2 or 3 experiences one of the cardiac conduction events listed below during the 144 hours after the Start of the First Infusion of Study Drug (SFISD):

- QTcF interval of  $\geq$  500 msec; or
- QTcF prolongation of  $\geq$  60 msec as compared to baseline; or
- Mobitz Type II second degree atrioventricular (AV) block; or
- Third degree or high grade AV block; or
- Polymorphic Ventricular Tachycardia;

If one of the listed safety events occurs in a patient who is receiving Auxora in Cohort 1 but the event is not thought to be dose limiting, 4 additional patients will be enrolled in Cohort 1 and randomized 3:1 to Auxora versus Placebo for a total of 8 patients enrolled in the cohort, 6 randomized to Auxora and 2 to Placebo. The PI

and CalciMedica will consult after all 8 patients are enrolled to determine if dose escalation to Cohort 2 will occur. If one of the listed safety events occurs in a patient who is receiving Auxora in Cohort 1 and the event is dose limiting, further dosing will not occur using the planned dose regimens but may occur using a regimen that provides lower total exposure of drug.

If one of the listed safety events occurs in a patient who is receiving Auxora in Cohort 2 but the event is not thought to be dose limiting, 4 additional patients will be enrolled in Cohort 2 and randomized 3:1 to Auxora versus Placebo for a total of 12 patients enrolled in the cohort, 9 randomized to Auxora and 3 to Placebo. The PI and CalciMedica will consult after all 12 patients are enrolled to determine if dose escalation to Cohort 3 will occur. If one of the listed safety events occurs in a patient who is receiving Auxora in Cohort 2 and the event is dose limiting, further dosing will not occur in either Cohorts 2 or 3. 4 additional patients may be enrolled in Cohort 1 and randomized 3:1 to Auxora versus Placebo.

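### The protocol and SAP give different sizes for Cohort 2: 4 patients expanding to 8 in the protocol, 8 expanding to 12 in the SAP

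*SAP*

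**What the plan says.** **Protocol, initial size.** Section 3.1 reads "If dose escalation occurs, the next 4 patients will be enrolled in Cohort 2 and randomized 3:1 to Auxora or Placebo", and the synopsis (Study Design) has the same number.

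**Protocol, expansion.** After a listed cardiac conduction event on Auxora that is judged not dose-limiting, section 3.1 says "4 additional patients will be enrolled in Cohort 2 and randomized 3:1 to Auxora versus Placebo" but prints no total. The synopsis prints it: "will be enrolled in Cohort 2 and randomized 3:1 to Auxora versus Placebo for a total of 8 patients enrolled in the cohort", split 6 Auxora and 2 placebo.

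**SAP, initial size.** Trial Design reads "If dose escalation occurs, the next 8 patients will be enrolled in Cohort 2 and randomized 3:1 to Auxora or Placebo".

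**SAP, expansion.** Interim Analysis and Stopping Guidelines adds 4 patients who "will be enrolled in Cohort 2 and randomized 3:1 to Auxora versus Placebo for a total of 12 patients enrolled in the cohort", split 9 and 3. It continues: "The PI and CalciMedica will consult after all 12 patients are enrolled to determine if dose escalation to Cohort 3 will occur".

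**Add-back.** Both documents allow a further optional step after a dose-limiting event in Cohort 3: "4 additional patients may be enrolled in Cohort 2 and randomized 3:1 to Auxora versus Placebo". The protocol gives these patients a different regimen; the SAP does not mention one.

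**Cap.** The synopsis says "Up to 32 patients with confirmed COVID-19 pneumonia on invasive mechanical ventilation randomized at up to two sites". Protocol section 6.1 repeats the 32 and provides for replacement of patients who do not reach the second BAL.

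**The concern.** The same cohort has two initial sizes, two expanded sizes and two trigger points for the consultation on Cohort 3. Neither text is an amendment log, and neither document says which prevails.

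Four things depend on the answer:

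- how many patients on the middle regimen are enrolled before escalation is decided;
- the precision of that arm's primary pharmacodynamic estimate, which matters because precision is the stated basis for the sample size;
- the number of placebo patients available for comparison;
- whether the cap of 32 is compatible with the design.

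The coordinating centre that maintains the SAP also prepares the cohort-stratified randomisation sequence. The documents do not show which version the list follows.

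**Working it through.** **Inputs.** Cohort sizes are from protocol section 3.1, the protocol synopsis, and the SAP's Trial Design and Interim Analysis sections. Allocation is taken as exactly 3:1.

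| | Protocol | SAP |
|---|---|---|
| Cohort 1 | 4, expanding to 8 | 4, expanding to 8 |
| Cohort 2 | 4, expanding to 8 | 8, expanding to 12 |
| Cohort 3 | 8, expanding to 12 | 8, expanding to 12 |
| Initial total | 4+4+8 = 16 | 4+8+8 = 20 |
| All cohorts expanded | 8+8+12 = 28 | 8+12+12 = 32 |
| Plus Cohort 2 add-back of 4 | 32 | 36 |
| Cohort 2 Auxora | 3, then 6 | 6, then 9 |
| Pooled placebo, initial | 1+1+2 = 4 | 1+2+2 = 5 |
| Pooled placebo, all expanded | 2+2+3 = 7 | 2+3+3 = 8 |

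**The cap.** The figure of 32 equals the SAP's fully expanded total. It also equals the protocol's fully expanded total plus the add-back. It therefore cannot show which size was meant. The last row needs all three cohorts to expand, then a dose-limiting event after Cohort 3 has reached 12, then use of the optional add-back. Replacements are not counted.

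**The plan's own precision figure.** Protocol section 10.1 and the SAP (Power Considerations) give a half-width of 0.77 SD with 9 per arm. The one-sample t half-width is t(0.975, n−1)/√n. At n = 9 it is 2.306/3 = 0.769, which reproduces 0.77.

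**The same formula at the Cohort 2 sizes.**

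- n = 3: 4.303/√3 = 2.48 SD (protocol, initial)
- n = 6: 2.571/√6 = 1.05 SD (protocol expanded, or SAP initial)
- n = 9: 0.77 SD (SAP, expanded)

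Add-back patients are left out of the arm because the protocol gives them another regimen.

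**Cohort 2 Auxora minus pooled placebo.** Assume the exploratory ANCOVA is fitted to three dose arms and one pooled placebo arm with a single baseline covariate. Assume also a common SD, no gain from the covariate and no chance baseline imbalance. Residual df = N − 5, and the half-width is t(0.975, N−5)·√(1/a + 1/b), where a is the number of Cohort 2 Auxora patients and b the number of pooled placebo patients.

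| | Protocol | SAP |
|---|---|---|
| Initial | N=16, df 11, 3 v 4: 1.68 SD | N=20, df 15, 6 v 5: 1.29 SD |
| Only Cohort 2 expanded | N=20, df 15, 6 v 5: 1.29 SD | N=24, df 19, 9 v 6: 1.10 SD |
| All expanded | N=28, df 23, 6 v 7: 1.15 SD | N=32, df 27, 9 v 8: 1.00 SD |

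**The case against.** The conflict itself is hard to dispute. The case on the other side is about how much follows from it.

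- **Splits.** Exact splits are printed only for expanded cohorts, and the SAP specifies blocks of varying size. If, as an assumption, a block of 8 opened a 4-patient cohort, the first four would split 3:1 with probability 40/70 (57%). This stands as a qualification: the initial splits of 3:1 and 6:2 are the intended ones, not guaranteed. The printed expanded splits support reading them that way.
- **The cap.** Reaching 36 takes a chain of events, and an optional add-back can be declined. That is fair. It is an extreme path, but neither document rules it out.
- **Comparative precision.** The primary analysis is descriptive, the ANCOVA is exploratory, and neither document says outright that placebo is pooled across cohorts. The difference half-widths are therefore illustrative. The within-arm figures do not need those assumptions.
- **The 9-per-arm statement.** It is not specific to Cohort 2. Initial Auxora arms are 3, 3 and 6 under the protocol and 3, 6 and 6 under the SAP, so no dose arm starts at 9 under either. It needs revisiting once sizes are agreed, but the contradiction did not create that problem.
- **Timing.** After an expansion, consultation is tied to enrolment, not to completed observation. The counts are therefore patients enrolled by that point.

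None of this reconciles the two sizes.

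**Conclusion.** The contradiction holds and is not a single slip. The SAP carries its version through the initial size, expanded total, split and consultation trigger, and the protocol is equally coherent with its own. The documents do not show which is intended.

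The version chosen moves the planned total by 4 patients and the Cohort 2 Auxora arm by 3. The initial within-arm half-width is more than twice as wide under the protocol as under the SAP. By ordinary expansion, Cohort 2 reaches the 9 patients used in the precision statement only under the SAP. These figures rest on exact 3:1 allocation and exclude replacements and add-back patients from the arm. The comparisons with placebo rest also on the ANCOVA assumptions stated with them.

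This should be corrected, because a sample size and an escalation trigger depend on it.

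**What to change.** Reconcile the synopsis, protocol section 3.1 and the SAP so that each states the same initial and expanded Cohort 2 size with its Auxora and placebo numbers, including the expanded total now missing from section 3.1. Which size is right is for the sponsor and investigators to decide.

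Then:

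- restate the 9-per-arm precision statement for the agreed arm sizes;
- check the cap of 32 against those sizes, including the add-back and replacements;
- confirm that the cohort-stratified randomisation list matches.

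The cost is wording edits wherever the agreed figures differ from the text, and a check of the list. The downside is that the stated precision may become less favourable and the cap may have to be restated.
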